#### **11.0 Risk/Benefit Analysis**

##### **11.1 Risk associated with SBRT for organ confined prostate cancer**

- 11.1.1** Acute toxicities reported to occur as a result of SBRT for prostate cancer include, but are not limited to: general malaise, bowel/bladder irritation, local hair loss, and/or local musculoskeletal pain
- 11.1.2** Late toxicities reported to occur as a result of SBRT for prostate cancer are primarily gastrointestinal including bleeding, ulceration, perforation, stenosis, and/or fistula and genitourinary including urethral stricture, bleeding, ulceration, and erectile dysfunction.

##### **11.2 Minimization of Risks**

Although the risks outlined in Section 10.3 may occur, the likelihood of serious events occurring is considered uncommon as long as certain precautions are taken. The potential risks have been minimized by:

- Premedication as described in Section 8.1, (e.g. rectal amifostine)
- Improved rectal dose profile with rectal balloon
- Strict compliance with normal tissue dose constraints as described in Sections 7.3

##### **11.3 Potential Patient Benefits**

- 11.3.1** Ability to offer effective and expedient local therapy
- 11.3.2** Reduction in amount of radiation delivered to adjacent normal structures compared to standard-fractionation radiation therapy
- 11.3.3** Significantly reduced treatment duration compared to standard-fractionation radiation therapy

##### **11.4 Justification of the Study**

For men diagnosed with localized prostate cancer, choosing between the various treatment options can be confusing and sometimes frustrating. For those who wish to avoid an invasive procedure, external beam radiotherapy which is fractionated daily over about two months has been the only alternative. Recent technological advances in stereotactic positioning of a patient for precise radiation delivery with online image guidance have led to a trend in radiation oncology of hypofractionation, which for the patient equals shorter treatment duration with the potential of equivalent or better tumor control

and toxicity rates. The use of hypofractionation in prostate cancer in particular is supported by its radiobiology; however, the proximity of adjacent organs at risk including the bladder and rectum has previously precluded its widespread adoption. When carefully administered, SBRT offers the potential to deliver the high doses necessary to control prostate cancer while sparing the adjacent structures in just five fractions.

### **11.5 Statistical Analysis**

**11.5.1** The overall survival and biochemical control rates will be analyzed.

**11.5.2** The incidence rate for any serious adverse events will be calculated.

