## **2.0 Objectives**

This study will evaluate the local control rate as well as acute and late toxicity rates of stereotactic body radiotherapy (SBRT) for the treatment of organ confined prostate cancer.

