### **2.1 Hypothesis**

- 2.1.1 For selected patients with localized prostate cancer (clinical stage T1-2N0M0), stereotactic body radiotherapy (SBRT) is technically feasible with acceptable complication rates.
- 2.1.2 Biochemical control with stereotactic body radiotherapy (SBRT) will be at least as good as standard fractionation radiation therapy

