### **2.2 Study Design**

- 2.2.1 Single site, non-randomized, prospective, phase IV trial
- 2.2.2 Study group will include organ confined prostate cancer
- 2.2.3 Data collected will include patient demographics, pathology data, tumor stage, SBRT dose fractionation scheme, dose received by adjacent critical normal tissues, tumor recurrence data, and acute and late toxicities.
- 2.2.4 Follow up data will be collected during the patient's standard office visits. The anticipated duration of this study is 5 years

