### **2.3 End Points**

- 2.3.1 Primary endpoints will be biochemical control rate
  - Serial blood tests for prostate specific antigen (PSA) levels will be obtained at regular intervals
  - The "Phoenix definition" for biochemical recurrence (nadir + 2 ng/ml) will be used
- 2.3.2 Secondary endpoint will be late toxicity rate.
  - Grading of acute and late complications is defined in Section 12.3 (Appendix III)

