## **10.3 Toxicity**

**10.3.1** The patient will fill out the American Urological Association (AUA) Symptom Score Sheet and Expanded Prostate Cancer Index Composite (EPIC) questionnaire for gastrointestinal, urinary and sexual quality of life. (14) (Appendix IV and Appendix V, respectively)

**10.3.2** The investigator will report and record all serious adverse events that occur. Adverse events should be reported using the CTC grading system (Appendix III).

**10.3.2** Examples of anticipated acute adverse events include:

- General malaise
- Urinary irritative or obstructive symptoms – dysuria, increased urinary frequency, nocturia, weak stream, hesitancy, and possible urinary retention
- Rectal irritation – loose stools, cramping, straining, hemorrhoidal inflammation
- Radiation dermatitis – dryness, tanning, redness, itching
- Localized hair loss
- Musculoskeletal pain

**10.3.3** Examples of anticipated late adverse events include:

- Bleeding, ulceration and/or perforation of the bladder, rectum, or small bowel
- Neurologic changes including motor weakness, numbness, paresthesias, and/or bowel or bladder dysfunction
- Persistent changes in bowel or bladder habits
- Small bowel obstruction
- Urethral stricture resulting in urinary retention
- Localized skin fibrosis, edema, and/or ulceration
- Erectile dysfunction
- Radiation-induced secondary malignancy

**10.3.4** Reporting of unanticipated or serious adverse events will be reported according to the institutions IRB policy. An unanticipated adverse event is defined as follows:

Any serious adverse effect on health or safety or any life-threatening problem or death caused by, or associated with, stereotactic body radiotherapy, if that effect, problem, or death was not previously identified in nature, severity, or degree of incidence in the investigational plan or application (including a supplementary plan or application), or

any other unanticipated serious problem associated with a treatment that relates to the rights, safety, or welfare of subjects.

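### Late toxicity rate is the only secondary endpoint, but the only toxicity analysis planned is serious adverse event incidence, with no acute/late boundary and incomplete late-event rows on the follow-up form

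*Combined protocol and SAP*

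**What the plan says.** Section 2.0 sets the aim: "This study will evaluate the local control rate as well as acute and late toxicity rates". Section 2.1.1 hypothesises that the treatment "is technically feasible with acceptable complication rates". Section 2.3.2 then states "Secondary endpoint will be late toxicity rate" and refers to Section 12.3 (Appendix III) for the grading of acute and late complications.

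Section 11.5 has two lines. The first covers overall survival and biochemical control. The second is the whole of the toxicity analysis: "The incidence rate for any serious adverse events will be calculated".

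On collection, 2.2.3 includes "tumor recurrence data, and acute and late toxicities". Section 10.3.2 adds "The investigator will report and record all serious adverse events that occur", and asks for adverse events to be graded by the CTC system. The follow-up form (Appendix VIII) has an ACUTE block and a LATE block, with columns for grade, timing, treatment and comments.

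**The concern.** An endpoint needs an analysis that estimates it. Late toxicity rate is the proportion of patients with a toxicity of stated severity in the late phase. Serious adverse event incidence counts serious events at any time after treatment starts. It mixes the two phases and leaves out late events that are troublesome but not serious.

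Three consequences follow. The endpoint has no planned estimate. If the late rate is defined after the data are seen, the phase boundary, the grade cut-off and the handling of pre-existing symptoms can each be chosen with the result in view. And the background series in Section 1.0, against which readers will judge acceptable complication rates, report toxicity by phase and grade, so an incidence of serious events is not directly comparable with them.

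**Working it through.** The documents state no sample size, power or event count, and give no figure to reproduce. The check sets the sections side by side, counts form rows, and ends with an illustration.

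**1. Endpoint against planned statistic**

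| | 2.3.2 endpoint | 11.5.2 statistic |
|---|---|---|
| Phase | late | any |
| Severity | not stated | serious only |
| Time point, denominator, estimator | not stated | not stated |

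**2. Acute/late boundary.** Section 12 is the reference list. Appendix III is Section 13.3 and gives CTCAE v3.0 severity grades with no time cut-off. Section 10.3 lists examples of acute and late events without a time. The Timing column and visit date on Appendix VIII allow an event to be dated, but no rule assigns the date to a phase.

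**3. Form coverage.** Appendix VIII has 10 ACUTE rows and 14 LATE rows. Mapping the 8 late event types in 10.3.3 to the LATE rows:

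| Late event type | LATE row |
|---|---|
| Bleeding, ulceration, perforation | six GI and GU rows |
| Neurologic change | motor and sensory neuropathy |
| "Persistent changes in bowel or bladder habits" | none; diarrhea, frequency/urgency and dysuria are under ACUTE only |
| Small bowel obstruction | GI Stricture (nearest row) |
| Urethral stricture with retention | GU Stricture |
| Skin fibrosis, edema, ulceration | none; radiation dermatitis is under ACUTE only |
| Erectile dysfunction | Impotence |
| Secondary malignancy | none in either block |

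Covered: 5 of 8, so 8 − 5 = 3 are not. If GI Stricture is not accepted for small bowel obstruction, 8 − 4 = 4 are not. The table has no row for other events. Appendix III grades skin fibrosis, secondary malignancy, urinary incontinence and urinary retention, yet none of these has its own row. The reverse holds for impotence: it has a row, but Appendix III has no grade for it.

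**4. Baseline.** In the 10.1 table, Toxicity Assessment has no pre-treatment mark. Diarrhea is graded against baseline and urinary frequency against normal in Appendix III. Incontinence and retention are not.

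**5. Illustration only.** The documents do not define serious by grade. Assume serious means grade 3 or higher, and use the late rates in Section 1.0.

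- 41-patient series, urinary: grade 3 in 2/41 = 4.9% (exact 95% CI 0.6% to 16.5%); grade II in 24%. If the 24% includes grade 3, the gap is 24 − 4.9 = 19.1 points. If it excludes grade 3, grade 2+ is 24 + 4.9 = 28.9% and the gap is 24.0 points.
- 41-patient series, bowel: 15% grade II against no grade 3, a gap of 15 points.
- 304-patient series, with rectal amifostine: urinary gap at most 2.0 points (35 Gy) or 5.8 points (36.25 Gy, 11 months); bowel grade 2+ at 35 Gy, nil.
- If half of the grade 2 urinary events were also serious, the gaps halve: 9.6 to 12.0 points in the first series, and 1.0 and 2.9 points in the second.

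**The case against.** The strongest reply is that the data are there. Adverse events are to be graded whether or not serious, each form row has Timing and Comments columns, and each form carries a visit date. An analyst could split the phases and compute a late rate, and a late bladder symptom could be entered in a row printed under ACUTE. This stands, and a reader who infers that late toxicity is not collected, or cannot be computed, goes too far. What is missing is the definition, the analysis and full capture.

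Other parts also stand:

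- 11.5 is not limited to serious events; it covers survival and biochemical control too. The gap concerns toxicity.
- The list in 10.3.3 is of examples and does not define the endpoint, so 3 of 8 measures form coverage and not lost events. Under-recording is plausible but not shown. Skin edema and ulceration can be partly graded under radiation dermatitis, and a second cancer would probably surface through the form's serious-event item.
- It would be wrong to say there is no baseline. History and physical examination, AUA and EPIC are all marked before treatment, and some Appendix III items already refer to baseline or normal. The gap is the clinician's grade for items such as incontinence and retention.

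None of this supplies an estimate of the secondary endpoint or a rule for phase.

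**Conclusion.** The point holds and should be fixed. Followed as written, 11.5.2 gives no estimate of the only secondary endpoint, no section separates acute from late, and the LATE block omits at least 3 of the protocol's own 8 example event types (4 on the strict mapping). These findings rest on the text and a row count, not on assumptions.

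The numerical size is not established. A reader might infer from the 41-patient series that the planned statistic would hide around 80% of late urinary toxicity of grade 2 or higher (19.1/24 = 80%; 24/28.9 = 83%). The documents do not support that as a forecast: it assumes serious means grade 3 or higher, the upper figure also assumes that grade 2 and grade 3 patients are different people, and the other cited series gives gaps from nil to 5.8 points. Serious acute events would also add to the planned statistic, in an amount the documents do not give.

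**What to change.** 1. **Section 11.5.2.** Add the late toxicity rate: the proportion of patients, or the cumulative incidence where follow-up varies, with 95% CI, having late CTCAE v3.0 grade 2+ and grade 3+ genitourinary and gastrointestinal toxicity that is new or worse than before treatment. Report it at 1 year, and later as follow-up allows, with numbers at risk. Treating death as a competing event is optional; item 11 of Appendix VIII records its date. List late skin toxicity and second malignancy descriptively. Report erectile dysfunction separately, for example from EPIC, because Appendix III does not grade it. Keep serious adverse event incidence, split by phase.
2. **Boundary.** State one acute/late analysis boundary tied to scheduled visits, so that each visit falls wholly in one phase. One example, which is my assumption: 6-week and 3-month visits acute, later visits late. Correct the cross-reference in 2.3.2 to Section 13.3.
3. **Appendix VIII.** Add LATE rows for urinary frequency/urgency, dysuria, retention, incontinence, diarrhea/bowel change, skin fibrosis/ulceration and secondary malignancy, plus a row for other events. Record a baseline grade for urinary and bowel items at the existing pre-treatment visit.
4. **Lesser and optional.** Add a descriptive summary of AUA and EPIC change from baseline to 1 year; no analysis of these is stated now.

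The cost is wording, seven named form rows plus the row for other events, and one baseline entry. Baseline grades not taken before treatment cannot be recovered reliably, so this part is best done early. The 10.1 visits are only suggested and the 1-year toxicity assessment is discretionary, so estimates will apply to patients assessed, and later ones may be imprecise. The late rate is likely to look less favourable than a serious-event rate.

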## **13.0 Appendices**

### **13.1 Appendix I**

## **13.2 Appendix II**

### **KARNOFSKY PERFORMANCE SCALE**

100	Normal; no complaints; no evidence of disease
90	Able to carry on normal activity; minor signs or symptoms of disease
80	Normal activity with effort; some signs or symptoms of disease
70	Cares for self; unable to carry on normal activity or do active work
60	Requires occasional assistance, but is able to care for most personal needs
50	Requires considerable assistance and frequent medical care
40	Disabled; requires special care and assistance
30	Severely disabled; hospitalization is indicated, although death not imminent
20	Very sick; hospitalization necessary; active support treatment is necessary
10	Moribund; fatal processes progressing rapidly
0	Dead

### **ZUBROD PERFORMANCE SCALE**

0	Fully active, able to carry on all pre-disease activities without restriction (KPS 90-100)
1	Restricted in physically strenuous activity but ambulatory and able to carry out work of a light or sedentary nature. For example, light housework, office work (KPS 70-80)
2	Ambulatory and capable of all self-care but unable to carry out any work activities. Up and about more than 50% of waking hours (KPS 50-60)
3	Capable of only limited self-care, confined to bed or chair 50% of more of waking hours (KPS 30-40)
4	Completely disabled. Cannot carry on any self-care. Totally confined to bed or chair (KPS 10-20)

13.3 Appendix III

**Common Terminology Criteria for Adverse Events v3.0 (CTCAE)**

	GRADE				
Toxicity	1	2	3	4	5
CONSTITUTIONAL					
Fatigue	Mild fatigue over baseline	Moderate or causing difficulty performing some ADL	Severe fatigue interfering with ADL	Disabling	-
Fever	100.4-102.2°F	102.3-104.0°F	> 104.0°F for < 24 hr	> 104.0°F for > 24 hr	Death
Weight loss	5 - < 10% of baseline	10 - < 20% of baseline	≥ 20% of baseline; tube feeding or TPN indicated	-	-
PAIN					
Pain due to radiation	Mild pain not interfering with function	Moderate pain: pain or analgesics interfering with function, but not interfering with ADL	Severe pain: pain or analgesics severely interfering with ADL	Disabling	-
Myositis (inflammation or damage of muscle)	Mild pain not interfering with function	Pain interfering with function, but not interfering with ADL	Pain interfering with ADL	Disabling	Death
SKIN					
Radiation dermatitis	Faint erythema or dry desquamation	Moderate to brisk erythema; patchy moist desquamation, mostly confined to skin folds and creases; moderate edema	Moist desquamation other than skin folds and creases; bleeding induced by minor trauma or abrasion	Skin necrosis or ulceration of full thickness dermis; spontaneous bleeding from involved site	
Telangiectasia	Few	Moderate number	Many and confluent	-	-
Ulceration	-	Superficial ulceration < 2 cm size; local wound care; medical intervention indicated	Ulceration ≥ 2 cm size; operative debridement, primary closure or other invasive intervention indicated (ex. Hyperbaric oxygen)	Life-threatening consequences; major invasive intervention (ex. Complete resection, tissue reconstruction, flap, grafting)	Death
Fibrosis	Increased density, "spongy" feel	Increased density with firmness or tethering	Increased density with fixation of tissue; operative intervention indicated; interfering with ADL	Life-threatening; disability; loss of limb; interfering with vital organ function	Death
Soft Tissue Necrosis	-	Local wound care; medical intervention indicated	Operative debridement or other invasive intervention indicated (ex. Hyperbaric oxygen)	Life-threatening consequences; major invasive intervention indicated (ex. Tissue reconstruction, flap, or grafting)	Death
NEUROLOGY					
Neuropathy: Motor	Asymptomatic, weakness on exam/testing only	Symptomatic weakness interfering with function, but not interfering with ADL	Weakness interfering with ADL; bracing or assistance to walk (e.g. cane or walker) indicated	Life-threatening; disabling (e.g. paralysis)	Death
Neuropathy: Sensory	Asymptomatic, lost deep tendon reflexes or paresthesia (including tingling), not interfering with function	Symptomatic alteration or paresthesia (including tingling), interfering with function, not interfering with ADL	Sensory alteration or paresthesia interfering with ADL	Disabling	Death

GI TRACT					
Nausea	Loss of appetite without alteration in eating habits	Oral intake decreased without significant weight loss, dehydration, or malnutrition; IV fluids indicated < 24 hr	Inadequate oral caloric or fluid intake; IV fluids, tube feedings, or TPN indicated $\geq$ 24 hr	Life-threatening consequences	Death
Vomiting	1 episode in 24 hr	2-5 episodes in 24 hr; IV fluids indicated < 24 hr	$\geq$ 6 episodes in 24 hr; IV fluids or TPN indicated $\geq$ 24 hr	Life-threatening consequences	Death
Diarrhea	Increase of < 4 stools per day over baseline; mild increase in ostomy output compared to baseline	Increase of 4-6 stools per day over baseline; IV fluids indicated < 24 hrs; moderate increase in ostomy output compared to baseline; not interfering with ADL	Increase of $\geq$ 7 stools per day over baseline; IV fluids indicated $\geq$ 24 hrs; hospitalization; severe increase in ostomy output compared to baseline; interfering with ADL	Life-threatening consequences (e.g., hemodynamic collapse)	Death
Enteritis	Asymptomatic, pathologic or radiographic findings only	Abdominal pain; mucous or blood in stool	Abdominal pain, fever, change in bowel habits with ileus; peritoneal signs	Life-threatening consequences (ex. Perforation, bleeding, ischemia, necrosis)	Death
Ulceration	Asymptomatic, radiographic or endoscopic findings only	Symptomatic; altered GI function (altered dietary habits, oral supplements); IV fluids indicated < 24 hr	Symptomatic and severely altered GI function (inadequate oral caloric or fluid intake); IV fluids, tube feedings, or TPN indicated $>$ 24 hr	Life-threatening consequences	Death
Bleeding	Mild, intervention (other than iron supplements) not indicated	Symptomatic and medical intervention or minor cauterization indicated	Transfusion, interventional radiology, endoscopic, or operative intervention indicated	Life-threatening consequences; major urgent intervention indicated	Death
Perforation	Asymptomatic radiographic findings only	Medical intervention indicated; IV fluids indicated < 24 hr	IV fluids, tube feedings, or TPN indicated $\geq$ 24 hr; operative intervention indicated	Life-threatening consequences	Death
Stricture	Asymptomatic radiographic findings only	Symptomatic; altered GI function (altered dietary habits, vomiting, bleeding, diarrhea); IV fluids indicated < 24 hr	Symptomatic and severely altered GI function (altered dietary habits, diarrhea, or GI fluid loss); IV fluids, tube feedings, or TPN indicated $\geq$ 24 hr; operative intervention indicated	Life-threatening consequences; operative intervention requiring complete organ resection	Death
Fistula	Asymptomatic; radiographic findings only	Symptomatic; altered GI function (ex. Altered dietary habits, diarrhea, or GI fluid loss); IV fluids indicated < 24 hr	Symptomatic and severely altered GI function (ex. Altered dietary habits, diarrhea, or GI fluid loss); IV fluids, tube feedings, or TPN indicated $\geq$ 24 hr	Life-threatening consequences	Death
GENITOURINARY					
Bladder spasms	Symptomatic, intervention not indicated	Symptomatic, antispasmodics indicated	Narcotics indicated	Major surgical intervention indicated (e.g., cystectomy)	
Cystitis	Asymptomatic	Frequency with dysuria; macroscopic hematuria	Transfusion; IV pain medications; bladder irrigation indicated	Catastrophic bleeding; major non-elective intervention indicated	Death
Fistula	Asymptomatic; radiographic findings only	Symptomatic; noninvasive intervention indicated	Symptomatic interfering with ADL; invasive intervention indicated	Life-threatening consequences; operative intervention requiring partial or full organ resection; permanent urinary diversion	Death
Incontinence, urinary	Occasional (e.g.,	Spontaneous, pads	Interfering with ADL;	Operative intervention	-

	with coughing, sneezing, etc.), pads not indicated	indicated	intervention indicated (e.g., clamp, collagen injections)	indicated (e.g., cystectomy or permanent urinary diversion)	
Urinary frequency/urgency	Increase in frequency or nocturia up to 2 x normal; enuresis	Increase >2 x normal but <hourly	≥1 x/hr; urgency; catheter indicated	-	-
Urinary retention	Hesitancy or dribbling, no significant residual urine; retention occurring during the immediate postoperative period	Hesitancy requiring medication; or operative bladder atony requiring indwelling catheter beyond immediate postoperative period but for <6 weeks	More than daily catheterization indicated; urological intervention indicated (e.g., TURP, suprapubic tube, urethrotomy)	Life-threatening consequences; organ failure (e.g., bladder rupture); operative intervention requiring organ resection indicated	Death
Stricture, GU	Asymptomatic, radiographic or endoscopic findings only	Symptomatic but no hydronephrosis, sepsis or renal dysfunction; dilation or endoscopic repair or stent placement indicated	Symptomatic and altered organ function (e.g., sepsis or hydronephrosis, or renal dysfunction); operative intervention indicated	Life-threatening consequences; organ failure or operative intervention requiring organ resection indicated	Death
MUSCULOSKELETAL					
Fracture	Asymptomatic, radiographic findings only	Symptomatic but non-displaced; immobilization indicated	Symptomatic and displaced; operative intervention indicated	Disabling	Death
METABOLIC					
Albumin	3-4 g/dL	2-2.99 g/dL	< 2 g/dL		Death
Alkaline phosphatase	> nl – 2.5 x nl	> 2.5 – 5 x nl	> 5 – 20 x nl	> 20 x nl	-
ALT	> nl – 2.5 x nl	> 2.5 – 5 x nl	> 5 – 20 x nl	> 20 x nl	-
AST	> nl – 2.5 x nl	> 2.5 – 5 x nl	> 5 – 20 x nl	> 20 x nl	-
Bilirubin	> nl – 1.5 x nl	> 1.5 – 3 x nl	> 3 – 10 x nl	> 10 x nl	-
Creatinine	> nl – 1.5 x nl	> 1.5 – 3 x nl	> 3 – 6 x nl	> 6 x nl	Death
SECONDARY MALIGNANCY	-	-	Non-life-threatening basal or squamous cell carcinoma of the skin	Solid tumor, leukemia, or lymphoma	Death

